- Participation in another clinical trial of experimental treatment (does not include studies e.g. randomising patients to one of more stent types for PCI and following patients registry-based). Patients included in the national trial of hydralazine and metformin for heart failure may also be included
- Contraindication for establishing implantable device treatment
- Previously implanted CRT system
- Does not wish to participate

Endpoints:

Primary:

- Death or non-planned hospitalisation for heart failure
 - Death
 - Non-planned hospitalisation for heart failure (non-planned hospitalisation >24 hours due to heart failure requiring intensified heart failure therapy)

Secondary:

- Sudden death
- Cardiac death
- Clinical response defined as "*increase in NYHA class (≥ 1 class from baseline) or improved walking distance by 6MWT ($\geq 10\%$ from baseline)*" after 6 and 24 months
- 6MWT, changes from baseline to follow-up after 6 and 24 months
- NYHA class, changes from baseline to follow-up after 6, and 24 months
- Quality of Life (QoL) and patient reported outcomes (PROs), changes from baseline to follow-up after 6, 12, 24 and 48 months
- Echocardiographic endpoints (re-modelling of LV: LVESV, LVEDV, LVEF). See supplementary protocol on imaging
- ICD therapy (time to first and number of appropriate and inappropriate ICD therapy, respectively, in addition as ATP and shock therapy, respectively)
- Time to first episode of VT/VF
- Persistent atrial fibrillation
- Recently diagnosed atrial fibrillation (>30 seconds recorded by the implanted device)
- Procedure time at implantation, fluoroscopy time and dose
- Number of LV leads used at implantation
- Device-related complications (periprocedural: lead re-operation, pneumothorax, hemothorax, pericardial bleeding/tamponade and later (30 days post implantation): LV lead re-operation, device replacement due to battery depletion, and infection requiring extraction)
- Battery longevity (measured by ¹number of device replacements during the study period due to battery depletion and ² device battery longevity + estimated remaining device battery longevity as reported by the device at last study follow-up)

Study design:

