Based on previous studies as well as data from the CRT population at Aarhus University Hospital, Skejby (n=1600) it is assumed that 35% of the population will reach the primary endpoint "death or non-planned hospitalisation for heart failure" within a period of 4 years. Based also on the above mentioned randomised controlled trial of 182 patients and up to 3 years of follow-up, and on the result of the DANISH study, this seems realistic (15). Half of these endpoints are expected to be deaths and the other half of non-planned hospitalisation for heart failure. To show a relative reduction of 25% in the incidence of this endpoint (to an absolute 26%) with $\alpha=0.05$ and $1-\beta=0.80$, n=432 patients must be included in each group. Given these

assumptions, 264 primary endpoints will occur during the study period. Assuming that no more than 10% of the patients withdraw during the study period, it will be sufficient to **include n=500 patients in each group**. Thus, a total of n=1000 patients need to be included in the study. The study is not designed to detect a significant reduction in mortality.

If, alternatively, one wanted to show a 20% reduction (from 35% to 28%), 719 patients should be included in each group (453 primary endpoints), 1500 patients in total. If one wanted to show a 30% reduction (from 35% to 24.5%) 315 patients should be included in each group, 700 in total.

Data analysis:

The primary analysis is carried out as an intention-to-treat analysis (patients randomised to the intervention group are compared with patients randomised to the control group without regard for their actual treatment). The primary data analysis will present time to the primary endpoint in Kaplan-Meier curves for each treatment group and if relevant stratification variable. Hazard ratio for reaching the primary endpoint in the intervention group relative to the control group is calculated by use of Cox regression model. Supplementary, restricted mean survival time is calculated.

Besides a non-adjusted analysis, also an analysis adjusted for age, gender, QRS morphology (LBBB/non-LBBB/RV paced), QRS width (≥ 150 ms / < 150 ms), NYHA class (II/III or outpatient IV), underlying disease (IHD/non-IHD determined heart failure), as well as including centre is done.

Subgroup analyses of the primary endpoint are planned for patients

- with different gender
- with higher and lower age (around the median)

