- with QLV (time from QRS start to local LV activation where the LV lead is positioned) above/below the median value, respectively
- in NYHA class II and III/outpatient IV, respectively, at baseline
- with baseline LVEF above/below the median value, respectively
- with ischaemic and non-ischaemic background for heart failure, respectively
- with LBBB and non-LBBB, respectively
- with upgrade from RV pacing to CRT and primary implantation of CRT, respectively
- with the RV lead in a septal and non-septal position, respectively (RV lead position determined by flash CT after implantation)

- with the RV lead in an apical and non-apical position, respectively (RV lead position determined by flash CT after implantation)
- with and without echocardiography detected dyssynchrony, respectively (radial time-to-peak, cross-correlation and pattern-analysis) of LV
- scar tissue/perfusion evaluation by CT scan. Total percentage of scar tissue (higher/lower than median) as well as impact of scar tissue localisation with regard to the site of LV lead position (LV lead close to scar (in or in neighbour-segment in a 17-segment model of LV) or remote to scar.

Analysis for statistical interaction is done with respect to the subgroup-analysis above and presented graphically in a Forest plot.

Secondary endpoints are compared in a similar way using Cox regression or multipel linear or logistical regression analysis. In datasets with repeated measures, ANOVA is used. Whether data are normally distributed or not and whether single or repeated data determinations exist are taken into consideration. If relevant, competing risk is adjusted for in the analyses.

A p-value <0.05 is considered significant in two-sided test.

Adjudication of endpoints:

Monthly during the study/follow-up, the study secretariat will verify vital status for all included patients through the Civil Registration System (CPR). In case of death, the centre following the patient will gather information on the death from the patient's GP and from other hospitals/departments, if relevant. This information will be forwarded to the study secretariat coordinating the adjudication of endpoints. A copy of the death certificate is obtained, unless the cause of death is known (e.g. during hospital admission).

The endpoint committee consists of the members of the steering committee.

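### No supplied text puts baseline 6MWT or PRO score into the models for these change-from-baseline secondary endpoints; stating it as a covariate would add precision at almost no cost

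*Combined protocol and SAP*

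**What the plan says.** All references are to the combined protocol and SAP unless stated otherwise.

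- **Endpoints, secondary.** Two sets of continuous outcomes are worded as changes: "6MWT, changes from baseline to follow-up after 6 and 24 months" and "Quality of Life (QoL) and patient reported outcomes (PROs), changes from baseline to follow-up after 6, 12, 24 and 48 months". (The amendment log in the Protocol document later drops the 12-month questionnaires, which does not affect this point.) LVESV, LVEDV and LVEF are listed as remodelling endpoints without being worded as changes, and the reader is sent to a supplementary imaging protocol.
- **Data analysis, primary endpoint.** Besides the unadjusted analysis there is "also an analysis adjusted for age, gender, QRS morphology (LBBB/non-LBBB/RV paced), QRS width". The list goes on to NYHA class, ischaemic or non-ischaemic disease, and centre. It is the only covariate list in the plan. It contains no baseline 6MWT, PRO score, LV volume or LVEF.
- **Data analysis, secondary endpoints.** "Secondary endpoints are compared in a similar way using Cox regression or multipel linear or logistical regression analysis". The next sentence assigns ANOVA to datasets with repeated measures. Neither sentence names a covariate or says what role the baseline value plays.
- **Follow-up and Patient-reported outcomes.** 6MWT and echocardiography are repeated at 6 and 24 months, and the questionnaires at baseline and several later visits. The ANOVA sentence may therefore govern all of them.

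**The concern.** Subtracting the baseline is not the same as adjusting for it. A change score fixes the coefficient of the baseline value at 1. Regression on the baseline estimates that coefficient, and it is usually below 1. Fixing it at the wrong value adds noise to the treatment contrast, and a chance baseline difference between the arms then carries through into the estimated effect.

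At stake is the precision of the functional and quality-of-life results. The Background section gives a reason to care: in the group's earlier 182-patient trial, clinical response differed between arms (74% vs 58%) while heart failure hospitalisation or death did not. The baseline values needed for the more precise analysis are already collected, because a change score cannot be formed without them.

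**Working it through.** **The plan's own figure.** The documents give no sample size, SD or correlation for any secondary endpoint. The only calculation is for the primary endpoint: "it is assumed that 35% of the population will reach the primary endpoint", reduced to 26%, two-sided alpha 0.05, power 80%, so that "n=432 patients must be included in each group". The standard two-proportion formula gives 410 per group, and with continuity correction 432. Events are 432 × (0.35 + 0.26) = 263.5, matching the stated 264. The figure reproduces but does not bear on this point.

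**Inputs**
- Two-sided 5% level: "A p-value <0.05 is considered significant in two-sided test".
- 500 randomised per group less 10% withdrawal (Sample size): 500 × 0.90 = 450 per arm. Deaths will lower this further. The variance ratios below do not depend on it.
- Correlation ρ between baseline and follow-up: **assumed**, 0.3 to 0.8.
- Follow-up SD divided by baseline SD, k: **assumed**, 1.0 or 1.2.
- 80% power for the change-score analysis: a reference point only, since the plan states no power for these endpoints.

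**Variance ratio.** In units of the baseline variance:
- change score: 1 + k² − 2ρk
- baseline-adjusted (ANCOVA): k²(1 − ρ²)

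With k = 1 the ratio is (1 − ρ²) / [2(1 − ρ)] = (1 + ρ)/2. The first expression minus the second is (1 − ρk)², which is never negative. It is zero only when ρk = 1, that is, when the slope of follow-up on baseline is exactly 1. The cost of estimating one extra coefficient with several hundred patients per arm is negligible.

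**Power after adjustment** = Φ[(1.960 + 0.842)/√ratio − 1.960].

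| ρ | Ratio, k = 1 | Power | Worth, per arm (450/ratio) | Ratio, k = 1.2 | Power |
|---|---|---|---|---|---|
| 0.3 | 0.65 | 93.5% | 692 | 1.3104/1.72 = 0.762 | 89.4% |
| 0.5 | 0.75 | 89.9% | 600 | 1.08/1.24 = 0.871 | 85.1% |
| 0.7 | 0.85 | 86.0% | 529 | 0.7344/0.76 = 0.966 | 81.3% |
| 0.8 | 0.90 | 84.0% | 500 | 0.5184/0.52 = 0.997 | 80.1% |

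At ρ = 0.5, k = 1 and 450 per arm, the difference detectable with 80% power falls from 2.802 × √(2/450 × 1.00) = 0.187 SD to 2.802 × √(2/450 × 0.75) = 0.162 SD.

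**Chance imbalance.** The 95% chance range for a baseline difference is ±1.96 × √(2/450) = ±0.13 SD. At ρ = 0.5 and k = 1, a difference of that size moves the unadjusted change contrast by (1 − 0.5) × 0.13 = 0.065 SD, about a third of 0.187 SD. Over repeated randomisations this averages to zero.

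**Do the listed covariates stand in for the baseline value?** Suppose they explain a share R² of both baseline and follow-up (assumed, acting equally on both). The remaining correlation is (ρ − R²)/(1 − R²), and the ratio is one plus that, halved. For ρ = 0.3, 0.5 and 0.7 it is 0.61, 0.72 and 0.83 at R² = 0.1, and 0.56, 0.69 and 0.81 at R² = 0.2. They do not replace it.

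**The ANOVA route.** If baseline is one of the repeated time points, the group-by-time contrast between baseline and a single visit is the difference in mean change, so the same loss applies. If baseline is a covariate, nothing is lost. The text does not say which is meant.

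**The case against.** The strongest reply is that the plan leaves the model open and does not prescribe an inefficient one. Several parts of that reply stand.

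- A reader might infer that the primary endpoint's covariate list is carried over to these endpoints and so excludes their baseline values. The documents do not say so. The similarity wording could refer to that list, to the unadjusted comparison or only to the general approach, and multiple linear regression does not rule out a baseline term. What can be said is that no supplied text includes the baseline value.
- A reader might infer that regression to the mean biases the change score. It does not: it affects both randomised arms alike, so only precision and chance imbalance are at issue.
- A reader might extend the point to LV volumes and LVEF as a finding. They are not worded as changes, and the imaging protocol was not among the documents supplied. The PRO-appendix was not supplied either, and it may say more about the questionnaires.
- A reader might count NYHA change among the affected endpoints. Baseline NYHA class is already in the list, and how it is grouped is a separate matter that is not pressed here.
- The gain cannot be fixed from the documents. The k = 1.2 columns show that no minimum gain can be promised.

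What does not stand is the idea that the ANOVA sentence settles the matter. Of the readings left open, only those with baseline as a covariate are efficient, and the text does not choose one.

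**Conclusion.** The point holds as a low-cost improvement in precision for 6MWT and the PRO scores. As written, the plan permits an unadjusted change score or an equivalent ANOVA contrast. Relative to a baseline-adjusted analysis, either has a variance 1/0.90 = 1.11 to 1/0.65 = 1.54 times as large, assuming equal SDs and ρ from 0.8 down to 0.3. With a follow-up SD 1.2 times the baseline SD, the penalty runs from almost nothing (ρ = 0.8) to 1/0.762 = 1.31 times (ρ = 0.3). Both ρ and the SD ratio are assumptions. What does not depend on them is that, at this sample size, adjustment is essentially never worse. The documents do not support reading this as a biased comparison or as a stated exclusion of baseline values. The primary endpoint and its sample size are untouched.

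**What to change.** In Data analysis, amend both the sentence on secondary endpoints and the ANOVA sentence after it. Changing only the first would leave two competing models for the same outcomes. Suggested content:

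- 6MWT and each PRO score are compared between randomised groups by linear regression (ANCOVA) at a single visit or, across visits, by a repeated-measures model of the post-baseline values.
- Each model includes the outcome's own baseline value as a continuous covariate and the randomisation stratum (true LBBB / other BBB / RV pacing).
- This is the leading analysis for these endpoints. The unadjusted change is reported descriptively.
- The same applies to LVESV, LVEDV and LVEF unless the imaging protocol already provides for it. If the imaging protocol or the PRO-appendix already names a model, cross-refer to it.

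The cost is a sentence or two and one added covariate per model. The stratum is close to the QRS morphology term already in the primary list. No new data, visits or patients are needed. Patients without a baseline value already drop out of a change score, so none are lost. The amendment log extends the study period through 31-12-2026; the wording should be fixed and dated before the randomised groups are compared on these endpoints.

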Hypothesis:

Targeted positioning of the LV lead to the CS branch with the latest local electrical LV activation reduces the incidence of the combined endpoint "death or hospitalisation for heart failure" compared to standard CRT implantation in patients with heart failure and prolonged QRS.

Aim:

To investigate, whether targeted positioning of the LV lead to the CS branch with the latest local electrical LV activation reduces the incidence of the combined endpoint "death or hospitalisation for heart failure" compared to standard CRT implantation in patients with heart failure and prolonged QRS.

Inclusion:

Patient must meet all the following criteria:

- Age >40 years
- Heart failure, NYHA II, III, outpatient IV
- LVEF \leq 35% measured by echocardiography
- In optimised medical treatment for heart failure*
- Branch block, defined as one of the following:
 - ¹"true LBBB" \geq 130ms (Definition of LBBB according to AHA/ACC/HRS Scientific Statement from 2009: QRS \geq 130 ms, "broad notched or slurred R wave in leads I, aVL, V5, and V6 (an occasional RS pattern in V5 and V6 may occur because of displaced transition of the QRS complex)", "absent q waves in leads I, V5, and V6", "normal R peak time in leads V1, V2, and V3 (if R waves are present) and >60 ms leads V5 and V6")
 - ²LBBB-similar, intraventricular conduction delay (IVCD), right bundle branch block (RBBB), all >150ms or
 - ³RV paced QRS and indication for upgrade to CRT (>50% RV pacing)
 - ⁴RV pacing indicated by bradycardia (primary implantation) and indication for CRT (heart failure, reduced LVEF \leq 35% prior to RV pacing and expected large percentage of RV pacing)
- Indication for primary CRT-D or CRT-P implantation or upgrade from RV pacing (pacemaker or ICD) to CRT-D or CRT-P.
- Ischaemic heart disease (IHD) or non-IHD

- Sinus rhythm or atrial fibrillation
- Life expectancy >2 years
- Signed informed consent

*: optimised medical treatment for heart failure means: treatment with target dose betablocker, ACE inhibitor/angiotensin receptor blocker/combination of ACE inhibitor - neprilysin inhibitor, and aldosterone receptor antagonist as indicated according to guidelines. If impossible to uptitrate one or more of the drugs to target dose, then treatment with maximum tolerated dose.

Exclusion criteria:

- NYHA class I
- AMI within the latest 3 months
- CABG within the latest 3 months
- Life expectancy <2 years

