In both treatment arms: In all patients, fluoroscopic images/film of the position in two planes (LAO 40-60° and RAO 30-40°) of the three leads is recorded and saved by the end of the procedure. Operation time (first

incision - last suture) and fluoroscopy time and dose are recorded. Time used for mapping of CS and positioning of the LV lead is recorded.

After implantation, the VV interval (the interval from pacing in the right ventricle until pacing in the left ventricle) is set for the narrowest possible QRS. The AV interval is set short enough to avoid fusion between the biventricular pacing and the intrinsic ventricular activation.

The day after the implantation, the delay of activation of LV where the LV lead is positioned is measured in all patients (at that time, the lead is expected to be in a stable position that might be a little different from immediately after the implantation). In LBBB patients the interval from RV sensing to LV sensing is measured, in all other patients RV pacing to LV sensing is measured (use device-programmer).

CT scan: In all patients, a contrast-enhanced CT scan for visualisation of the CS branches and later definition of LV scar tissue is done prior to implantation. Moreover, a flash CT scan without contrast is done in all patients after implantation, prior to discharge for a precise determination of the lead positions (14). In patients with significantly reduced renal function (estimated GFR $<30\text{ml/min/1.73 m}^2$) the pre-operative contrast-enhanced CT is omitted, but the post-operative CT without contrast is done.

Randomisation 1:1, stratified for ^atrue LBBB, ^bother BBB and ^cRV pacing (identification of the latest activated LV segment may be especially important in patients without true LBBB). Randomisation is done web-based in the case-record form used for data collection. Block-randomisation is used to ensure that each centre includes a similar number of patients in each treatment group (blocks of 10+10 for LBBB and RV pacing, 5+5 for other BBB). Randomisation takes place after informed consent has been obtained and before device implantation.

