Blinding: The implanting physician knows the randomisation arm in order to provide the correct treatment. The patients will not know the randomisation arm. Follow-up is done equally in the two treatment groups, by other health personnel than the implanting physician, and blinded for randomisation and treatment (intervention or control). The primary endpoint and cause of death is adjudicated by an endpoint committee blinded for randomisation and treatment (intervention or control).

Recruitment/obtaining informed consent:

Eligible study candidates are found among patients who are admitted for CRT implantation and meet the inclusion criteria. Typically, the first contact will be made in the department the day before the procedure. A short oral introduction will be given by a doctor or nurse related to the study. If the potential candidate is interested, an informative interview is scheduled. The patient is advised about the right to have an observer present at this interview (a family member, a friend, or a member of the staff with no relation to the study). The written information is handed over to ensure that the patient has sufficient time for reading prior to the interview. The informative interview takes place in the patient's ward and is carried out by a doctor or nurse related to the study. If the interview can not be undisturbed in the ward, it is done in another quiet place. During the interview the patient will have sufficient time to listen to the oral information and ask questions. It will be possible to have at least 24 hours for reflection before giving informed consent. A copy of the written consent is handed over to the patient.

Follow-up:

Patients are followed prospectively and primary and secondary endpoints recorded. Clinical follow-up is scheduled after 3, 6 and 12 months, subsequently annual appearance. Moreover, all patients are followed by remote monitoring of their CRT device. This ensures early detection of technical issues and some clinical problems and is current standard for CRT-D devices.

Echocardiographic follow-up plus 6MWT and NYHA classification is scheduled after 6 and 24 months. See supplementary protocol on study imaging.

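### Time to first VT/VF and sudden death are compared without planned device type (CRT-D or CRT-P); stratifying by it is a small and nearly free improvement

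*Combined protocol and SAP*

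**What the plan says.** All references are to the combined protocol and SAP.

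- **Secondary endpoints (Data analysis):** "Secondary endpoints are compared in a similar way using Cox regression or multipel linear or logistical regression analysis". No covariate is specified for any individual secondary endpoint.
- **Primary endpoint (Data analysis):** "Besides a non-adjusted analysis, also an analysis adjusted for age, gender, QRS morphology (LBBB/non-LBBB/RV paced), QRS width", followed by NYHA class, ischaemic or non-ischaemic disease, and centre. Device type is not in this list, nor among the planned subgroups.
- **Randomisation:** "Randomisation 1:1, stratified for ^atrue LBBB, ^bother BBB and ^cRV pacing". Device type is not a stratum. On timing: "Randomisation takes place after informed consent has been obtained and before device implantation".
- **Inclusion:** "Indication for primary CRT-D or CRT-P implantation or upgrade from RV pacing (pacemaker or ICD) to CRT-D or CRT-P". Both device types are enrolled, and the indication exists before allocation.
- **Endpoints, Secondary:** sudden death and "Time to first episode of VT/VF" are both listed.
- **Background:** whether pacing at the latest-activated site is pro-arrhythmic is described as unsettled.

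**The concern.** VT/VF and sudden death are the endpoints closest to the open pro-arrhythmia question. A defibrillator detects, stores and treats VT/VF, so having one plausibly raises the number of recorded episodes. It can also turn a sudden death into a treated episode. Planned device type is therefore likely to be a strong baseline predictor of recorded VT/VF, and to act in the opposite direction on sudden death.

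Leaving a strong predictor out of a Cox model has two consequences. The treatment hazard ratio is pulled towards 1, which costs some power. A chance difference in CRT-D share between the arms also enters the estimate, where it can resemble an arrhythmic effect or hide one. If such a difference appeared, a decision to adjust for it would be made after it was seen unless the plan had already settled the matter.

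**Working it through.** **The plan's own figures.** None is given for VT/VF, sudden death or CRT-D share. The stated 432 per group does reproduce (35% vs 26%, two-sided 0.05, 80% power, continuity-corrected), and 432 × (0.35 + 0.26) = 263.5 matches the 264 events. Those figures concern the primary endpoint only.

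**Inputs from the documents.** 500 patients per arm; two-sided 0.05; at least 2 years of follow-up after the last inclusion, in a 6-year study. Half of the 35% primary events are expected to be deaths, so 4-year mortality is about 17.5%.

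**Assumed inputs.** CRT-D share 40% to 80%; VT/VF and sudden-death rates by device type as shown below; follow-up either a fixed 4 years or uniform over 2 to 6 years.

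**Step 1: chance imbalance.** The SD of the between-arm difference in CRT-D share is √(2p(1−p)/500). At p = 0.5 this is √0.001 = 0.0316, so 2 SD is about 6.3 points. At p = 0.8 the SD is 0.0253.

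**Step 2: shift in the unadjusted hazard ratio.** Let h be the CRT-D to CRT-P hazard ratio for the endpoint and d the imbalance. The unadjusted hazard ratio is multiplied by about [1 + (p + d/2)(h − 1)] / [1 + (p − d/2)(h − 1)]. With p = 0.5 and d = 0.0632:

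| Assumed 4-year rate, CRT-D vs CRT-P | h | Factor |
|---|---|---|
| VT/VF 30% vs 5% | ln 0.70 / ln 0.95 = 6.95 | 4.163/3.787 = 1.10 |
| VT/VF 30% vs 10% | ln 0.70 / ln 0.90 = 3.39 | 2.271/2.120 = 1.07 |
| VT/VF 25% vs 15% | ln 0.75 / ln 0.85 = 1.77 | 1.409/1.361 = 1.04 |
| Sudden death 2% vs 6% | ln 0.98 / ln 0.94 = 0.33 | 0.642/0.685 = 0.94 |

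With h from 2 to 5 and shares of 50% to 80%, the factor at the 95% limit is 1.03 to 1.09 for VT/VF. With h of 0.5 to 0.7 it is 0.96 to 0.98 for sudden death. Simulation at 40% to 60% CRT-D gave VT/VF shifts of 4% to 12%. Together the range is about 3% to 12% for VT/VF and 2% to 6%, downwards, for sudden death. After stratification the VT/VF shift was about 0% to 2%.

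**Step 3: standard error, error rate and power.** Cox models were simulated with n = 1000 and 1,500 trials per scenario.

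- *Standard error of the log hazard ratio (null), without vs with device type:* 0.142 vs 0.142 for VT/VF at 20%; 0.288 vs 0.288 for sudden death at 5%. There is no change.
- *Without device type:* type I error 3.9% to 4.6%; coverage 94% to 96%.
- *VT/VF, true hazard ratio 1.5:* with h = 3, mean log hazard ratio 0.399 vs 0.409 and power 86.1% vs 87.9%. With h = 5, 0.384 vs 0.409 and 83.7% vs 87.5%.
- *VT/VF, true hazard ratio 1.4, follow-up 2 to 6 years, competing death:* at 30% vs 5%, the unadjusted hazard ratio averages 1.37 to 1.38. Power rises from 49% to 54% (40% CRT-D) or from 65% to 69% (60% CRT-D). At 30% vs 10% the gain is 2 to 3 points; at 25% vs 15% it is under 1 point.
- *Sudden death, true hazard ratio 1.5:* power 33.8% vs 34.1%.

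**Step 4: error given a 2-SD imbalance.** With no treatment effect, 50% CRT-D and the imbalance fixed at 6.3 points, the unadjusted VT/VF test rejects in about 8% (30% vs 5%), 7% (30% vs 10%) and 5.5% (25% vs 15%) of trials. The stratified test stays near 5%, with a mean hazard ratio of 1.00.

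**The case against.** The case against is strong on size. Four stronger readings are tempting, and none is supported.

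- **A reader might infer that precision is lost.** It is not: the Cox standard error is the same with and without device type. The loss is attenuation, and the power that goes with it.
- **A reader might infer that the hazard ratios are biased by imbalance.** Under 1:1 randomisation an imbalance is chance error that the confidence interval already covers on average. The simulated power figures already average over it, so the 2-SD shift is not an additional loss. What stands is that the error rate given a large observed imbalance is not 5%, and large imbalances are uncommon.
- **A reader might infer from the Follow-up section that VT/VF is detected differently by device type**, because remote monitoring "is current standard for CRT-D devices". The sentence before it says that all patients are remotely monitored, so the section does not support this.
- **A reader might infer that the plan prescribes the primary covariate list for these endpoints.** It says only that the approach is similar, and for the primary endpoint that list accompanies a non-adjusted analysis. The point does not depend on this, since device type is absent either way.

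Three further objections stand. Every figure compares against an unadjusted model; age, aetiology and centre in the adjusted model may absorb part of the device effect. The assumed range includes a negligible gain. Stratifying also does not settle how VT/VF is ascertained in CRT-P patients, which the documents leave unstated.

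**Conclusion.** The point holds as a minor, low-cost improvement, not as an error in the plan. Planned device type is available before allocation, plausibly predicts recorded VT/VF strongly, and is not a stratum, covariate or subgroup. Standard errors, average type I error and coverage are not harmed by omitting it.

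For VT/VF, the cost against an unadjusted model is slight attenuation, about 0 to 5 points of power, and exposure to a shift of about 3% to 12% at a 2-SD imbalance. For sudden death there is almost no power to gain, and the shift is about 2% to 6% downwards when the intervention arm has more CRT-D patients. It is included mainly for consistency.

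All sizes rest on assumed CRT-D shares, event rates and device effects. The gain over the covariate-adjusted model would be smaller and has not been computed.

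**What to change.** Before unblinding, add to the secondary-endpoint paragraph of Data analysis: *The Cox models for time to first VT/VF and for sudden death are stratified by planned device type (CRT-D/CRT-P) as recorded before randomisation. The CRT-D share is reported by arm.*

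Use the planned type, not the device implanted: the implanting physician knows the allocation, so only the planned type is certain to be a baseline variable.

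Hazard ratios by device type may be shown as description only. At 400 to 600 CRT-P patients and an assumed 5% rate there would be about 20 to 30 events, and a standard error of the log hazard ratio near 2/√25 = 0.4.

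The cost is one sentence and one two-level stratum, with no added patients or procedures. The inclusion criterion is met by either indication, and the documents do not say that the planned type is entered in the CRF before randomisation. If it is not, it would have to be taken from records made before randomisation.
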